8.2 Exclusion Criteria

1. Extended wear (sleeps in lenses one or more nights per week).
2. Any anterior segment infection, inflammation, disease, or abnormality that contraindicates contact lens wear as determined by the Investigator.

3. Any use of systemic medications or ocular medications for which contact lens wear could be contraindicated, as determined by the Investigator, including use of any topical ocular medications that would require instillation during contact lens wear.
4. Monocular subjects (only 1 eye with functional vision) or subjects fit with only 1 lens.
5. A known sensitivity to any ingredients in OFPM.
6. Biomicroscopy findings observed during the Visit 1 slit-lamp examination that are moderate (grade 3) or worse in either eye.
7. Prior refractive surgery (eg, LASIK and PRK).
8. History of herpetic keratitis, ocular surgery, or irregular cornea.
9. A pathological dry eye that precludes contact lens wear.
10. Use of mechanical eyelid therapy or eyelid scrubs within 14 days before Visit 1 and not willing to discontinue during the study.
11. Enrollment of the Investigator or his/her staff, family members of the Investigator, family members of the Investigator's staff, or individuals living in the households of these individuals.
12. Enrollment of more than 1 member of the same household in the study.
13. Participation in any clinical study within 30 days of Visit 1.
14. Subjects who are currently using or have not discontinued RESTASIS, XIIDRA or a topical steroid within the past 7 days.

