9 TREATMENTS ADMINISTERED

Upon completing the Pre-screening Questionnaire and satisfying the relevant pre-screening criteria, subjects will sign informed consent and then be considered enrolled into the study. A subject ID number will be assigned to enrolled subjects by entering the subject into the electronic data capture (EDC) system. Subjects eligible after Screening at Visit 1 will be randomized (1:1) to receive either OFPM or HMPS to care for their lenses in Period 1 of the study. For Period 2, the contact lens solution that was not allocated for use in Period 1 will be dispensed. Throughout the study, designated unmasked site personnel at the investigational site will be responsible for the accounting of all study products and will ensure that the study products are not used in any unauthorized manner.

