9.1 Identity of Study Treatments

Investigational Product: OFPM

Control Product: HMPS

OFPM will be supplied in sterile 10 fl. oz. (300 mL) filled bottles with investigational labelling. A new lens case will be supplied with each bottle.

Table 9-1 Study Treatments

Properties	OFPM (Test product)	HMPS (Control product)
Administration	Subjects will use OFPM to store and disinfect their contact lenses as instructed by the study team member(s) dispensing the solution and according to the instructions for use.	Subjects will use their HMPS to store and disinfect their contact lenses as instructed by the study team member(s) dispensing the solution and according to the instructions for use.
Duration of Treatment	The subject will wear their habitual lens brand (following manufacturer recommended replacement) on a daily wear modality for 30 ± 3 days using OFPM daily to care for their lenses.	The subject will wear their habitual lens brand (following manufacturer recommended replacement) on a daily wear modality for 30 ± 3 days using their habitual solution daily to care for their lenses.
Quantity/Dosage	Up to 32 cleaning and disinfecting cycles will be used for the study.	Up to 32 cleaning and disinfection cycles will be used for the study.
Supply	OFPM will be supplied sterile, in 10 fl. oz. (300 mL) filled bottles	HMPS will either be: 1) Purchased by the subject and

Properties	OFPM (Test product)	HMPS (Control product)

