11.7 Safety Analysis

The safety endpoints for this study are AEs, biomicroscopy findings, and device deficiencies.

Descriptive summaries (counts and percentages) for ocular and nonocular AEs will be presented by Medical Dictionary for Regulatory Activities (MedDRA) Preferred Terms. In addition to an overall presentation of AEs, reports will be generated for serious AEs. AEs leading to study discontinuation will be identified. Individual subject listings will be provided, as necessary.

Individual subject listings will be provided for AEs that occur after signing informed consent but prior to exposure to study lens care solutions.

Each biomicroscopy parameter will be tabulated by its grade. For each biomicroscopy parameter, counts and percentages of eyes that experience an increase of ≥ 2 grades from baseline to any subsequent visit will be presented. Baseline is defined as Visit 1. A supportive listing will be generated which will include all biomicroscopy data from the affected visit for those eyes experiencing the increase of ≥ 2 grades, with the following variables: lens care solution, Investigator, subject, age, sex, visit, eye, parameter, baseline value, and value at the visit.

Two listings (prior to exposure of investigational products, and treatment-emergent) of device deficiencies, as recorded on the *Device Deficiency* Form, will be provided. Additionally, each device deficiencies category will be tabulated.

No inferential testing will be done for safety analysis.

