### 5.3.1 Adverse Events

The applicable definition of an Adverse Event (AE) is in the study protocol. All AEs occurring from when a subject signs informed consent to when a subject exits the study will be accounted for in the reporting.

Analysis and presentation of pre-treatment AEs will be separated from treatment-emergent AEs occurring during the study period. A pre-treatment AE is an event that occurs after signing informed consent but prior to exposure to the study lens care for period 1 and period 2. The period for treatment-emergent AE analysis starts from exposure to the study lens care for period 1 and period 2 until the subject completes or is discontinued from the study.

Descriptive summaries (counts and percentages) for ocular and non-ocular AEs will be presented by Medical Dictionary for Regulatory Activities (MedDRA) Preferred Terms. In addition to an overall presentation of AEs, reports will be generated for special classes of AEs such as treatment-related AEs and serious AEs. AEs leading to study discontinuation will be identified. Presentation of ocular AEs will be by eye.

Individual subject's listings will be provided for both pre-treatment and treatment-emergent AEs.

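### Ocular adverse events are to be presented by eye, and no count or percentage of affected subjects is planned, although each subject uses the assigned solution for both lenses

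*SAP*

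**What the plan says.** SAP 5.3.1 sets out the AE tables as follows: "Descriptive summaries (counts and percentages) for ocular and non-ocular AEs will be presented by Medical Dictionary for Regulatory Activities (MedDRA) Preferred Terms". It adds reports for special classes, among them treatment-related and serious AEs, and then states the unit for ocular events: "Presentation of ocular AEs will be by eye". It gives no denominator. Subject-level information appears in the same section as individual listings of pre-treatment and treatment-emergent AEs.

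Protocol 11.7 promises the same kind of table ("Descriptive summaries (counts and percentages) for ocular and nonocular AEs will be presented") and names no unit. The synopsis is also silent on the unit.

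Exposure is set at subject level. Under Protocol 9, eligible subjects "will be randomized (1:1) to receive either OFPM or HMPS to care for their lenses in Period 1 of the study", and they receive the other solution in Period 2. Table 9-1 has the subject use the assigned solution for their lenses. Exclusion 4 in Protocol 8.2 removes "Monocular subjects (only 1 eye with functional vision) or subjects fit with only 1 lens". Each exposed subject therefore brings two exposed eyes to each solution used.

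The safety set (Protocol 11.2.1, SAP 2.1) is worded in terms of both subjects and eyes, classified by the product actually used.

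**The concern.** For a lens-care solution, a natural safety question is how many users had an ocular problem on each product. The subject is the unit that is randomized and exposed. A table in eyes answers a different question, and the answer to the first cannot be recovered from it. Six people with a reaction in both eyes and twelve people with a reaction in one eye give the same eye count.

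Safety is descriptive throughout (Protocol 11.7, SAP 5.2), so these tables are the planned safety summary and no model or test supplies the missing figure. The side effects listed in Protocol 5.2 are mainly ocular, so a difference between solutions would be expected to show in the ocular AE tables. What is at stake is how those tables are read.

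**Working it through.** The documents state no figure for this point, so there is none to reproduce. The check asks what a by-eye table can and cannot tell the reader.

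**Inputs**
- Two exposed eyes per subject (exclusion 4, Protocol 8.2).
- N = 120 subjects per solution, or 240 eyes. Protocol 8 plans about 120 randomized and about 110 completed, so the number exposed to a given solution may be somewhat lower. N cancels from the ratio below.
- k = number of subjects with the event on that solution. Not given; 3, 6 and 12 are assumed.
- b = share of those k subjects with the event in both eyes. Not given; the full range 0 to 1 is used.
- Each affected eye is counted once per table row (assumption; the SAP gives no counting rule).

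**Reading 1: percentage over all exposed eyes**

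Subject percentage = k/N. Affected eyes = k(1+b). By-eye percentage = k(1+b)/(2N). The ratio of by-eye to subject percentage is therefore (1+b)/2.

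| Affected subjects (N = 120) | % of subjects | % of eyes, b = 0 | % of eyes, b = 0.5 | % of eyes, b = 1 |
|---|---|---|---|---|
| 3 | 2.5 | 1.25 | 1.88 | 2.5 |
| 6 | 5.0 | 2.5 | 3.75 | 5.0 |
| 12 | 10.0 | 5.0 | 7.5 | 10.0 |

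The ratio is 0.5 when every event is in one eye, 0.75 when half the affected subjects have it in both, and 1.0 when all do. It never exceeds 1.

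Working back from the table, 12 affected eyes of 240 is 5.0% of eyes. That could be 6 subjects (6/120 = 5.0%), 12 subjects (12/120 = 10.0%) or any number between.

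**Reading 2: separate right-eye and left-eye columns, each over N**

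With R right eyes and L left eyes affected, the number of affected subjects lies between max(R, L) and R + L. With R = L = 6, each column shows 6/120 = 5.0%, and the subjects affected number 6 to 12 (5.0% to 10.0%). A single column can fall below half the subject percentage. Twelve one-eyed cases split 4 right and 8 left show 4/120 = 3.3% and 8/120 = 6.7%, against 12/120 = 10.0% of subjects.

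**Comparison between solutions (Reading 1)**

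The ratio of by-eye percentages, one solution to the other, equals the ratio of subject percentages times (1+b₁)/(1+b₂), where b₁ and b₂ are the values for the two solutions. If b₁ = b₂ the factor is 1 and the comparison is undistorted. With 12 affected subjects on each solution, b₁ = 0.5 and b₂ = 0.25, the by-eye figures are 18/240 = 7.5% and 15/240 = 6.25%, a factor of 1.5/1.25 = 1.2. The largest possible factor, 2, needs b₁ = 1 and b₂ = 0.

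**The case against.** The case against giving this much weight is substantial, and most of it stands.

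- **The SAP does not say that eyes are the only unit.** A reader might infer that subject counts are ruled out. They are not: the sentence sets a unit without excluding another, and the safety set is worded for subjects and eyes alike. But defining the set in both units does not promise a subject-level ocular table, and no readable sentence does.
- **A reader might infer that the tables will understate incidence by half.** That holds only if eyes are pooled and every event is one-eyed. The SAP fixes neither the layout nor the denominator, and the documents give no value for b. A percentage of eyes is also a correct statement about eyes.
- **A reader might infer a twofold bias between solutions.** That needs opposite extremes of b on the two solutions. Both are tabulated by the same rule, and in a crossover largely the same people use both. Where b does differ, more eyes really are affected on one solution, and a subject-only table would hide that.
- **A reader might see a conflict with Protocol 11.7, or an error in using different units for ocular and non-ocular events.** Section 11.7 names no unit, so nothing contradicts it. Biomicroscopy changes are already counted in eyes, and a non-ocular event has no eye to be counted by.
- **No data are lost and no decision turns on this.** Listings are planned, and at 3 to 12 affected subjects a count from them is feasible. Safety has no hypotheses, and the SAP's success criterion rests on CLDEQ-8 alone.

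What remains is that a planned summary table should not leave the reader to rebuild the number of people affected from listings.

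**Conclusion.** The point holds as a gap in the planned tables, at minor priority. If the stated rule is followed as written, the number of subjects with an ocular AE on each solution can only be bounded.

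Under pooled eyes the by-eye percentage is between 0.5 and 1.0 times the subject percentage, depending wholly on b. Under separate eye columns the subject count is known only to lie between the larger column and the sum of the two. These bounds assume two exposed eyes per subject, which exclusion 4 supports, and one count per affected eye, which is an assumption. They do not depend on N or on the event rate.

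The documents do not support a claim that incidence will be understated by any particular amount, or that the comparison of solutions will be biased.

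**What to change.** In SAP 5.3.1, keep the by-eye presentation, state its denominator, and add a sentence along these lines: *For each lens care solution, the number and percentage of subjects with at least one treatment-emergent ocular AE will also be given, by Preferred Term, with subjects exposed to that solution as the denominator.* Apply the same to the serious and treatment-related AE reports. Classification by the product actually used already follows from SAP 2.1.

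The by-eye figures should stay because they show whether events occur in one eye or both, which a subject count alone would hide. The cost is a few lines of SAP text and slightly wider ocular AE tables. No new data are needed, because the listings already hold AEs by subject.

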### **5.3.2 Biomicroscopy Findings**

Baseline is defined to be Visit 1. Each biomicroscopy parameter will be tabulated by its grade, at Baseline and Day 30. A shift table showing grade at baseline relative to Day 30 will also be presented for each parameter. For each biomicroscopy parameter, counts and percentages of eyes that experience an increase of  $\geq 2$  grades from baseline to any subsequent visit will be presented. A supportive listing will be generated which will include all biomicroscopy data from the affected visit for these eyes experiencing the increase of  $\geq 2$  grades, with the following variables: lens care solution, Investigator, subject, age, sex, visit, eye, parameter, baseline value, and value at the visit.

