11	Unmasked coordinator to assign/dispense the study lens care solution for Period 1 per randomization scheme. 1) HMPS purchased by the subject or provided by the site –or- 2) Investigational Masked OFPM Kit with Kit #. Educate on instructions for use.
12	Assess and record any adverse events (AEs) that are reported or observed from the time of informed consent (see Section 12).
13	Record any device deficiencies that are observed or reported.
14	Schedule Visit 2 (Period 1 Follow-up) to take place on Day 30 ± 3 days (scheduled 29 (± 3) days after Visit 1. Provide subject with Visit 2 reminder instructions: 
 The subject should bring the used lens case for the study period, along with their dispensed study lens care product used during the study period.

10.2.2 VISIT 2 – PERIOD 1/Day 30 & PERIOD 2/DAY 1

1	Document wear time compliance (days, hours) and lens care compliance. Collect used study lens care product from the subject.
2	Obtain information on any changes in medical health and/or the use of concomitant medications since Visit 1.
3	Have subject complete the Subjective Questionnaire based on lenses worn and study solution used during the 30 day study period (CLDEQ-8, [REDACTED] [REDACTED] [REDACTED])
4	Conduct Snellen VA with worn lenses. For details refer to MOP.
5	[REDACTED]

6	Remove lenses and perform biomicroscopy assessments using slit-lamp examination scales. For details and order of staining procedures, refer to MOP.
7	Perform subjective (manifest) refraction assessment and BCVA assessment (as needed). For details refer to MOP.
8	Assess and record AEs that are observed or reported (see Section 12).
9	Record any device deficiencies that are observed or reported.
10	Dispense a new pair of habitual lenses and perform Snellen VA with new lenses being dispensed at the visit. For details refer to MOP. For two-week replacement lens wearers, provide the subject an extra pair of study lenses for replacement at two weeks. Contact the subject at approximately 15 ± 1 days of the study period to remind the subject to replace their lenses and document date of replacement in the source.
11	Unmasked coordinator to assign/dispense the study lens care solution for Period 2 per randomization scheme. 1) HMPS purchased by the subject or provided by the site –or- 2) Investigational Masked OFPM Kit with Kit #. Educate on instructions for use.

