11.2 Analysis Data Sets

11.2.1 Safety Analysis Set

Safety analyses will be conducted using the safety analysis set on a treatment-emergent basis. The safety analysis set will include all subjects/eyes exposed to the newly dispensed habitual lenses for the study disinfected with at least one study lens product evaluated in this study. For treatment-emergent safety analyses, subjects/eyes will be categorized under the actual lens care product exposed.

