## **2            Analysis Sets**

### **2.1            Safety Analysis Set**

The safety analysis set will include all subjects/eyes exposed to the newly dispensed habitual lenses for the study disinfected with at least one study lens product evaluated in this study. Safety analysis will be conducted using the safety analysis set on a treatment-emergent basis. For treatment-emergent safety analysis, subjects/eyes will be categorized under the actual lens care products exposed.

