### 4.1 Efficacy Endpoints

#### Primary Endpoint

The primary endpoint is the score (range 0 to 37) from CLDEQ-8, obtained by adding the numerical responses to each of the 8 items, collected at the Day 30 follow up, for each product (Visit 2 and Visit 3).

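### With Visit 1 as the only biomicroscopy baseline, a Period 1 rise still present at Visit 3 would be counted under both solutions if the counts are split by solution

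*SAP*

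**What the plan says.** SAP 5.3.2 sets the biomicroscopy reference: "Baseline is defined to be Visit 1". Protocol 11.7 does the same, presenting eyes with an increase of 2 or more "grades from baseline to any subsequent visit will be presented. Baseline is defined as Visit 1". The SAP adds a second display: "A shift table showing grade at baseline relative to Day 30 will also be presented for each parameter". Flagged eyes go into a listing with these variables: "lens care solution, Investigator, subject, age, sex, visit, eye, parameter, baseline value, and value at the visit".

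On attribution, SAP 2.1 says that in treatment-emergent safety analysis "subjects/eyes will be categorized under the actual lens care products exposed". Protocol 11.2.1 matches it: "For treatment-emergent safety analyses, subjects/eyes will be categorized under the actual lens care product exposed".

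The design is a two-period crossover. Protocol 10.2.2 titles Visit 2 as "PERIOD 1/Day 30 & PERIOD 2/DAY 1", and Visit 3 is scheduled 29 (± 3) days later. SAP 4.1, defining the primary endpoint, shows that Day 30 occurs once per product: the score is "collected at the Day 30 follow up, for each product (Visit 2 and Visit 3").

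Neither document gives a Period 2 reference grade for biomicroscopy or says how a Period 1 finding that is still present in Period 2 is to be attributed.

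**The concern.** A baseline taken once, before either solution, is a sensible reference for asking whether an eye is worse than at entry. It is a poor one for asking under which solution the eye became worse. If the 2-grade counts are shown by solution, a finding that arose in Period 1 and has not resolved by Visit 3 is charged to both solutions, although nothing changed in Period 2. The Day 30 shift table for Period 2 carries the finding forward in the same way.

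Safety has no hypotheses (SAP 5.2) and no inferential testing (protocol 11.7), so readers will compare the columns by eye. A table that charges one solution's findings to the other misleads that comparison.

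**Working it through.** The documents state no figure for biomicroscopy rises, so there is none to reproduce. The check has two parts.

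**1. What the rule does to single eyes.** Grades are at Visits 1, 2 and 3. The Visit 1 column applies the stated rule by solution.

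| Path | Visit 1 rule | Visit 2 as Period 2 baseline | Visit 1 rule, Period 2 split by Visit 2 status |
|---|---|---|---|
| 0, 2, 2 | both periods | Period 1 only | Period 1; Period 2 row 'met at Visit 2' |
| 0, 1, 2 | Period 2 | not flagged | Period 2 row 'not met at Visit 2' |
| 2, 0, 2 | not flagged | Period 2 | not flagged |
| 0, 2, 0 | Period 1 | Period 1 | Period 1 |
| 0, 2, 4 | both periods | both periods | Period 1; Period 2 row 'met at Visit 2' |

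The double count is not confined to one odd path. Exclusion criterion 6 limits the Visit 1 grade to 2. On an assumed integer 0–4 scale there are 3 × 5 × 5 = 75 paths. Those flagged at both follow-up visits number 9 (Visit 1 grade 0) + 4 (grade 1) + 1 (grade 2) = 14. These are path counts, not probabilities.

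**2. What it does to the rates.** Inputs from the documents: about 110 completers, hence 220 eyes; 1:1 randomization, hence 110 eyes per sequence; no washout. Assumed, because the documents give no values: new-rise rates a and b per period for solutions A and B, and shares q_a and q_b of each solution's Period 1 rises still present at Visit 3.

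Eyes flagged under A = 110a (Period 1) + 110(a + q_b·b) (Period 2). Dividing by 220:

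- reported A = a + q_b·b/2
- reported B = b + q_a·a/2
- reported difference = (a − b) − (q_a·a − q_b·b)/2

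This ignores eyes with both a persisting and a new rise. Treating the periods as independent changes the rates below by at most 0.04 × 0.01 / 2 = 0.02 percentage points.

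*Equal persistence* (q_a = q_b = q): the difference becomes (a − b)(1 − q/2). With a = 4% and b = 1%:

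| q | Eyes A v B | Reported A v B | Difference (points) |
|---|---|---|---|
| 0 | 8.8 v 2.2 | 4.00% v 1.00% | 3.00 |
| 0.1 | 8.9 v 2.6 | 4.05% v 1.20% | 2.85 |
| 0.25 | 9.1 v 3.3 | 4.125% v 1.50% | 2.625 |
| 0.5 | 9.35 v 4.4 | 4.25% v 2.00% | 2.25 |
| 1 | 9.9 v 6.6 | 4.50% v 3.00% | 1.50 |

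In the sequence that starts with A, Period 2 flags under B are 110(b + q·a). At q = 0.25 that is 2.2 eyes, of which 1.1 were carried over; at q = 0.5 it is 3.3, of which 2.2 were. With 2% v 1% and q = 0.5 the table reads 2.25% v 1.50%.

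*Unequal persistence:*

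- a = b = 2%, q_a = 1, q_b = 0: A reads 2%, B reads 2% + 2%/2 = 3%. A gap is created.
- a = 2%, b = 1.5%, q_a = 0, q_b = 1: A reads 2% + 1.5%/2 = 2.75%, B reads 1.5%. A true gap of 0.5 points reads as 1.25.

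**3. What the split recovers.** Add the Period 1 eyes to the Period 2 eyes that did not meet the criterion at Visit 2. With independent periods, A gives [a + a(1 − b)]/2 = a − ab/2, and B gives b − ab/2. At 4% v 1% that is 3.98% v 0.98%, a difference of 3.00 points. No persistence term appears, so this holds whether or not q_a and q_b are equal.

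**The case against.** The strongest objection is that the split by solution is inferred. That stands: neither SAP 5.3.2 nor protocol 11.7 states it, and if each eye is counted once over the whole study there is no double count. But such a count would not compare the solutions, so the plan should say which is meant.

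A second objection is that safety analyses are treatment-emergent, so an unchanged finding would not be charged to the second solution. SAP 5.3.1 defines that term for adverse events only. For biomicroscopy both documents give an explicit rule, Visit 1 to any later visit, and the general wording does not override it.

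Third, other outputs show part of the picture. This also stands. Protocol 12.2 requires clinically relevant untoward changes to be reported as adverse events, grades are tabulated separately, and the listing gives solution, visit and eye. A carried-forward eye can be traced by matching rows, although the counts themselves do not separate it.

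Three stronger readings are tempting and are not supported:

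- *The Visit 1 baseline is an error or a contradiction.* The documents agree on it, and it is a legitimate reference. Replacing it with Visit 2 for Period 2 would miss 0, 1, 2 and flag 2, 0, 2.
- *The tables must make the solutions look more alike.* That needs equal persistence, which the documents do not establish.
- *The per-solution counts are the whole safety result.* The adverse event reports, grade tables and listing say otherwise.

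**Conclusion.** The point holds conditionally and is minor. If the 2-grade counts and shift tables are presented by solution, the rule as written counts a persisting Period 1 rise under both solutions. That follows from the single baseline and the absence of washout.

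The size cannot be drawn from the documents. At 4% v 1% with equal persistence, the shift is under half an eye per solution at q = 0.1; at q = 0.5 the lower rate doubles from 1% to 2%. Near q = 0 it is negligible, and subjects who exit at Visit 2 have no Visit 3 reading to carry a finding forward. The order of the solutions does not reverse in the equal-persistence examples; with unequal persistence the error can go either way.

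A reader might infer that the trial's conclusion is at risk. It is not: success rests on CLDEQ-8, and only descriptive safety tables are touched.

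**What to change.** Keep Visit 1 as the baseline and add to SAP 5.3.2 and protocol 11.7:

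> Eyes with an increase of 2 or more grades from Visit 1 will be presented by lens care solution in use at the visit. Eyes meeting the criterion at Visit 3 or at an unscheduled Period 2 visit will be shown in two rows per parameter: those that met the criterion at Visit 2, and those that did not meet it at Visit 2. The Period 2 shift table will footnote the number of eyes meeting the criterion at Visit 2.

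Sorting on Visit 2 status also places an eye flagged only at an unscheduled Period 1 visit that recovers and is flagged again in Period 2. A 0, 2, 0 eye counts only in Period 1 unless it is flagged at an unscheduled Period 2 visit.

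The cost is one extra row per parameter and one footnote. No new data are needed: protocol 10.2.2 has biomicroscopy at step 6, before the Period 2 solution is dispensed at step 11. Protocol 11 already allows a change to the analysis plan to be made by amendment or described in the clinical study report.

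There are limits. A 0, 2, 4 eye falls in the row for eyes that met the criterion at Visit 2 although it worsened in Period 2; the listing shows this. Carried-forward 1-grade shifts stay unmarked. The split shows when a finding appeared, not what caused it.

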10.3 Unscheduled Visits

Any visit that occurs between the regularly scheduled visits must be documented in the unscheduled visit pages of the eCRF. During all unscheduled visits, the following procedures should be conducted:

- Document wear time compliance (days, hours) and lens care compliance.
- Obtain information on any changes in medical health and/or the use of concomitant medications.
- Perform Snellen VA with lenses (as needed).
- Perform subjective (manifest) refraction (as needed).
- Perform BCVA assessment (as needed).
- Perform biomicroscopy.
- Record any AEs or device deficiencies that are observed or reported.
- Replace lenses and dispense additional study lens care solution for the study period if needed (as needed). Record all unplanned lens replacement dates in the source.
- Exit the subject from the study (if subject is discontinuing at the unscheduled visit).

If the subject is discontinuing at the unscheduled visit, the Early Exit visit eCRF should be completed rather than the eCRF form for an unscheduled visit.

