10.4 Discontinued Subjects and Screen Failures

Discontinued subjects are those who withdraw or are withdrawn from the study after being randomized. Subjects may discontinue from the study at any time for any reason. Subjects

may also be discontinued from the study at any time if, in the opinion of the Investigator, their continued participation poses a risk to their health. Discontinued subjects will not be replaced (ie, their subject numbers will not be re-assigned/re-used).

If a subject is identified not to fulfill the eligibility criteria for study inclusion during the Screening visit (Visit 1), the subject will be screen failed and will not participate any further in the study. The EDC system will be updated to confirm the subject is a screen failure. The Investigator will explain to the subject the reason(s) why eligibility was not met and provide appropriate information/treatment, if required. The Exit form will be completed for all discontinued subjects and screen failures.

Should a subject exhibit any clinically relevant signs, symptoms, or other clinical observations that possibly could be associated with suspected sensitivity or intolerance to one of the study treatments, the Investigator must document those observations on an AE Form. Observations must also be reported for occurrences not associated with any study treatment (see Section 12.3, Procedures for Recording and Reporting AEs and SAEs).

Any subject who exits early from the study should undergo all procedures outlined at Visit 3/Exit. Additionally, the Exit Form must be completed and the reason for discontinuation must be identified and captured in EDC.

Finally, to ensure the safety of all subjects who discontinue early, Investigators should assess each subject and, if necessary, advise them of any therapies and/or medical procedures that might be needed to maintain their health.

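### The SAP's biomicroscopy tables and listing leave out a rise from grade 2 to grade 3 that is seen only at an unscheduled visit, and possibly at an early exit

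*SAP*

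**What the plan says.** SAP 5.3.2 specifies three biomicroscopy summaries and one listing.

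- **Grade table:** "Each biomicroscopy parameter will be tabulated by its grade, at Baseline and Day 30".
- **Shift table:** "A shift table showing grade at baseline relative to Day 30 will also be presented for each parameter".
- **Rise count:** the number and percentage of eyes that worsen by 2 or more grades at any visit after baseline. Protocol 11.7 has the same rule, for eyes rising by 2 or more "grades from baseline to any subsequent visit will be presented. Baseline is defined as Visit 1".
- **Listing:** "A supportive listing will be generated which will include all biomicroscopy data from the affected visit for these eyes experiencing the increase of" 2 or more grades.

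Three other parts of the protocol bear on what these outputs can show.

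- Exclusion 6 (section 8.2) bars entry for "Biomicroscopy findings observed during the Visit 1 slit-lamp examination that are moderate (grade 3) or worse in either eye".
- Section 10.3 lists "Perform biomicroscopy" for all unscheduled visits, without the as-needed qualifier that refraction, BCVA and Snellen acuity carry there.
- On early exit, section 10.4 says: "Any subject who exits early from the study should undergo all procedures outlined at Visit 3/Exit". Section 10.3 adds that for a subject who discontinues at an unscheduled visit, "the Early Exit visit eCRF should be completed rather than the eCRF form for an unscheduled visit".

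Neither document says whether unscheduled or early-exit records enter the Day 30 tables.

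**The concern.** The outputs are restricted in two different ways. The tables show every grade, but only at Day 30. The rise count and its listing cover every visit, but only for changes of at least 2 grades. A one-grade change away from Day 30 falls between them.

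For most one-grade changes this matters little. The change from 2 to 3 is the exception, because it takes an eye to the level that the protocol does not accept at entry. Unscheduled and early-exit visits are also the ones that a problem is likely to prompt. The any-visit summary could show no eyes worsening under a solution although an eye on that solution had reached grade 3.

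**Working it through.** No stated figure needs reproducing here. The check applies the SAP 5.3.2 rules to every possible worsening.

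**Inputs**
- Baseline grade b: 0, 1 or 2, since exclusion 6 removes grade 3 and above.
- Later grade p: up to 4. The 0 to 4 scale in whole grades is an assumption. The grading scale is in the manual of procedures, and the documents say only that grade 3 is moderate.
- Visit type: Day 30 (Visits 2 and 3), unscheduled, or early exit.

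**Rules**
- Rise count and listing: the eye appears if p − b ≥ 2, at any visit.
- Grade and shift tables: the eye appears at any grade, at Day 30 only.
- The eye is missed if p − b < 2 and the record is not a Day 30 record.

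**Result at a visit that is not Day 30**

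| Change | p − b | In rise count and listing? | Reaches grade 3 or worse? |
|---|---|---|---|
| 0 to 1 | 1 | No | No |
| 0 to 2 | 2 | Yes | No |
| 0 to 3 | 3 | Yes | Yes |
| 0 to 4 | 4 | Yes | Yes |
| 1 to 2 | 1 | No | No |
| 1 to 3 | 2 | Yes | Yes |
| 1 to 4 | 3 | Yes | Yes |
| **2 to 3** | **1** | **No** | **Yes** |
| 2 to 4 | 2 | Yes | Yes |

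Six changes cross from grades 0–2 to grade 3 or worse. Five are reported and one, 2 to 3, is not. That result does not depend on where the scale begins or ends, because 3 − 2 = 1 on any whole-grade scale.

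**By visit type, for the 2 to 3 change**
- *Day 30:* shown in the grade and shift tables.
- *Unscheduled:* in no SAP 5.3.2 output, unless the eye is still at grade 3 at that period's Day 30 visit.
- *Early exit:* in no SAP 5.3.2 output if the record stays separate; in both tables if it is assigned to Day 30. The SAP does not say which.

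**Size of the early-exit group.** The protocol plans about 120 randomized and about 110 completed: 120 − 110 = 10 subjects, 10/120 = 8%, or up to 2 × 10 = 20 eyes. This is the planned number of non-completers, not an estimate of missed findings. The documents give no rate for unscheduled visits and no distribution of baseline grades, so the number of affected eyes cannot be derived.

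**The case against.** The strongest reply is that an eye missing from SAP 5.3.2 is not lost to the report.

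- **Listings.** The protocol synopsis promises subject listings giving details of every safety variable, and nothing in the SAP withdraws that. Protocol 11.7 tabulates by grade without naming a visit. This stands: a reader might infer that the eye appears in no listing at all, but the documents support only that it is absent from the SAP 5.3.2 listing. A general listing still gives no count by solution.
- **Adverse events.** Protocol 12.2 makes an untoward change in a study parameter reportable when the Investigator finds it clinically relevant, whatever the cause. Protocol 10.4 sends relevant signs of suspected intolerance to the AE form. SAP 5.3.1 presents ocular AEs by eye and identifies those leading to discontinuation. This would probably catch many such eyes, especially those that exit because of the finding. It depends on judgment, however, and counts the eye under a MedDRA term rather than a grade.
- **Early exit.** These subjects undergo the Visit 3 procedures, and the visit schedule labels Visit 3 as the Period 2 Day 30 and exit visit. A separate eCRF is a data-capture instruction, not an analysis rule. This stands: the early-exit gap is conditional.
- **Severity of what is missed.** A reader might infer that the worst cases drop out. They do not. The 2-grade rule is not limited to Day 30, and it catches every larger worsening and every arrival at grade 4.
- **Status of grade 3.** A reader might take grade 3 as the trial's safety limit. Exclusion 6 is an entry criterion, and the documents set no post-baseline threshold.

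**Conclusion.** The gap is real but narrow. For an unscheduled visit it follows directly from the text: a 2 to 3 change that is gone by Day 30 enters no table or listing in SAP 5.3.2. For an early exit it holds only if the record is not assigned to Day 30. Both scheduled post-baseline visits are Day 30 visits, so only these two situations are exposed.

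The conclusion rests on whole-number grading and on a literal reading of the SAP. It does not show that such eyes go unreported, or that a one-grade rise is the usual way to reach grade 3; the documents have no data on that. Safety is descriptive, without hypotheses or inferential tests, and the criterion for study success is unaffected. This is a minor, optional improvement.

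**What to change.** In SAP 5.3.2 and protocol 11.7:

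1. Keep the Day 30 shift table and add one built on the worst post-exposure grade within each period, including unscheduled and early-exit visits, by the solution in use.
2. For each parameter, add the count and percentage of eyes with any post-baseline grade of 3 or worse, by solution. This is a reporting cut only and sets no rule for managing subjects.
3. Extend the supportive listing to these eyes, or carry the synopsis commitment to list every safety variable into the SAP.
4. State whether early-exit and unscheduled records enter the Day 30 tables.

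With items 1 and 2, all 6 crossings to grade 3 or worse are reported at every visit type, instead of 5 of 6 at an unscheduled visit. The cost is a few table rows per parameter and a changed listing filter. The data are already collected, so nothing changes for sites or subjects.
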